Chronic pain is a serious problem in the US that affects 116 million adults¹. A number of chronic pain conditions can be linked both epidemiologically and biologically with various anxiety disorders^{2,3}. It is well known that anxiety can increase pain and that many patients with pain exhibit increased anxiety. Standard treatment options for chronic pain include prescribed pharmaceuticals and physical therapy. Anxiety is most commonly treated with prescribed pharmaceuticals and psychotherapy. A major gap in the development of effective therapies has been the lack of focus on the interaction between pain and anxiety disorders. That is, treatment of pain but not anxiety, or vice versa, is likely not as effective as treatment of both disorders or sets of symptoms at the same time. Fortunately, a number of integrative therapies, such as exercise and meditation, have been shown to be effective in separate studies for both pain and anxiety. Exercise is analgesic, is anxiolytic, low cost, and has many positive side-effects. Similarly, meditation has demonstrated efficacy in the context of chronic pain and anxiety. A therapy regimen consisting of both exercise with mindfulness meditation in these patient populations may produce greater benefits but it is currently unknown whether this combination of treatment is feasible. Issues of interest in developing a combined treatment regimen that is feasible to implement include: patient adherence and acceptance and the use of appropriate measures to assess symptoms following intervention. Before exploring this combined treatment approach in a full clinical trial, we will first determine the feasibility of this intervention in persons with spinal low back pain.

Our overall objective is to investigate the feasibility of an intervention that combines exercise and guided meditation in individuals with back pain. We will also investigate the feasibility of using a standard set of non-invasive human pain tests for predicting change in symptoms following intervention. These objectives are necessary in order to achieve our long-term goal of determining prescribed exercise/meditation protocols with the best cost-to-risk ratio as a therapy for improving symptoms in patients with chronic pain and comorbid anxiety. Our central hypothesis is that a combined exercise and meditation protocol will be feasible in this clinical population as indicated by high recruitment rates, subject retention, and treatment acceptance.

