Activity		-15 min meditation -30 min exercise (In clinic)	-15 min meditation -30 min exercise	Rest	Rest				
Day		23	24	25	26	27	28	29	
Activity		-15 min meditation -30 min exercise (In clinic)	-15 min meditation -30 min exercise	Rest	Pain Assess and Exit Survey (In clinic)				

while the subjects complete these forms. Basic health information obtained from the subject will assess whether the subject has been diagnosed with any cardiac, respiratory, neurological or musculoskeletal disorder, chronic pain or currently has acute pain (AHA health questionnaire). Subjects who report any of the above medical diagnoses or pain (with the exception of chronic low back pain) during screening will be excused from participation in the study. Subjects who cannot walk independently without a device will be excused from participation as well. Any identifying information used to determine eligibility, including the checklist of inclusion/exclusion criteria and the health questionnaires, will be destroyed.

Each trial is designed to last 29 days including an intake session and a post-meditation/exercise pain testing session. Pain testing is performed during the intake session (baseline) and on day 29 (48 hours after the last intervention). See **Figure 1** for illustrative time-line of individual trials for individuals assigned to the meditation then exercise group. Analogous time-lines will be used for exercise only subjects (30 minutes of exercise each day and 15 minutes of audiobook), meditation only subjects (15 minutes of meditation each day and 30 minutes of audiobook) or negative control subjects (15 minutes of audio book followed by 30 minutes of rest each day).

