This clinical trial will test the methodology and trial retention of one version of a combined therapy (along with comparison control groups). The combination of meditation and exercise will be done sequentially. This methodology is termed (1) Meditation first & then Exercise (Med&Exer). All participants in this exploratory trial will receive the therapeutic intervention, or one of three control options (negative control, meditation only, exercise only) (**Table 1**). We describe below the details of the interventions.

Table 1 – Experimental Conditions	
Experimental Condition	Description
Negative control	In clinic or at home, listen to an audiobook for ~15 minutes followed by 30 minutes of rest (including survey assessments)
Meditation only control	In clinic or at home, 15 minutes of meditation and listen to an audiobook for ~30 minutes (including survey assessments)
Exercise only control	In clinic or at home, listen to an audiobook for ~15 minutes (including survey assessments) then exercise (treadmill) for ~30 minutes
Meditation & then exercise (Med&Exer)	In clinic or at home, 15 min of meditation followed by 30 min of exercise (treadmill) plus survey assessments

Exercise in this exploratory study will consist of 30 minutes of moderate-intensity treadmill walking (starting at 3.5 mph and adjusted up or down to reflect moderate intensity for each individual participant) in the Rangos Human Testing Facility (Fisher Hall) on a treadmill with auto-shut off and integrated heart rate monitor (Polar H1 Heart Rate Sensor) on day 2 (first day of intervention), day 9, day 16, and day 23. During the other intervention days (day 3-6, 10-13, 23-27) participants will have the option of completing trials at Duquesne or “at home.” At home is defined as a participant using a personal treadmill or going to a community fitness center (e.g. YMCA). This “at home” component is designed to reduce the extra burden for patients who would otherwise have to travel to Duquesne for 22 total sessions (20 days of intervention plus intake and outtake sessions). Exercise will

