be performed 5x per week (1x per day) for a total of four weeks with two days of rest between the four exercise runs. Participants in the exercise-only group and Med&Exer will be encouraged to exercise when the gym is less busy. Any trials done in the Rangos Human Testing Facility will be done with the researcher in the room, monitoring the participant. Walking speed has been prescribed based on a standard equation incorporating metabolic equivalent of the task (METs). METs are a measure of an individual's energy exertion during a physical activity. The speed of treadmill walking was set to ensure energy expenditure falls within the moderate-intensity range (3.00-5.99 METs). Heart rate is monitored continuously before, during, and after exercise.

To evaluate the effect of the meditation on the participants, they will complete the Freiburg Mindfulness Inventory (FMI) meditation survey immediately prior to their first meditation before exercise. The FMI will be used again on day 27.

All participants will receive a 45 min meditation and stress training session following baseline pain testing (see Assessment section below) on the intake day (Day 1). These training sessions, done by clinical Psychologist [name] (Counseling and Wellbeing Center), discuss the potential of and use of mindfulness and meditation (in the meditation groups only) or about stress management for chronic pain (in the exercise only and negative control group). On subsequent "intervention" days, guided meditation recordings will be used for the two relevant meditation participant groups. Participants will listen to a 15 min guided meditation with mindfulness recording. We have 5 recordings, which will be pre-loaded on a MP3 player (see URLs for Recordings at the end of this Protocol). The participants will be allowed to take this MP3 player home with them if they choose to perform "at-home" trials.

Subjects will perform their exercise session with the researcher in the room, monitoring their heart rate and level of exertion. For subjects exercising "at home," we will instruct the subjects on warning signs to indicate that they should stop exercising. Subjects will be advised to place a chair near the treadmill to sit and rest if they become over-exerted.

4. Instruments

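### The 30-minute slot that replaces exercise is an audiobook in meditation-only but rest in the negative control, which confounds that comparison and any factorial or interaction estimate

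*Protocol*

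**What the plan says.** Protocol Table 1 (Experimental Conditions, section 3) defines four arms by a 15-minute block and a 30-minute block:

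- Negative control: "listen to an audiobook for ~15 minutes followed by 30 minutes of rest (including survey assessments".
- Meditation-only: "15 minutes of meditation and listen to an audiobook for ~30 minutes (including survey assessments".
- Exercise-only: "listen to an audiobook for ~15 minutes (including survey assessments) then exercise (treadmill) for ~30 minutes".
- Med&Exer: "15 min of meditation followed by 30 min of exercise (treadmill) plus survey assessments".

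The paragraph on time-lines in section 3 agrees. It describes "meditation only subjects (15 minutes of meditation each day and 30 minutes of audiobook" and "negative control subjects (15 minutes of audio book followed by 30 minutes of rest each day". Neither place explains why the two non-exercise arms have different fillers.

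Section 4 expects each of exercise, meditation and the combination to reduce disability. Section 8 plans effect sizes for comparisons of means, to inform a large-scale trial. The SAP tests MedExT against one control group, does not say which arm that is, and describes itself as covering one report from a larger study.

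**The concern.** The arms form a two-by-two layout: meditation yes or no, exercise yes or no, with fillers to keep session time similar. The 15-minute block is matched, because an audiobook replaces meditation in both arms without meditation. The 30-minute block is not matched, because what replaces exercise depends on whether the participant meditates.

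Meditation-only versus negative control then differs in two respects: meditation against audiobook for 15 minutes, and audiobook against rest for 30 minutes. If listening to a story affects pain, anxiety or disability differently from resting, that effect is credited to meditation. It also enters, with the opposite sign, any estimate of whether the two components reinforce each other.

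This matters because the protocol's rationale is comparative ("A therapy regimen consisting of both exercise with mindfulness meditation in these patient populations may produce greater benefits"), and because a meditation effect size from this trial may be carried into the planning of the next one.

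**Working it through.** No sample size, SD or effect size is needed. The question is which quantities four arm means can identify.

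**Inputs** (Table 1, confirmed by the text of section 3):

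| Arm | 15-minute block | 30-minute block |
|---|---|---|
| Negative control (N) | audiobook | rest |
| Meditation-only (M) | meditation | audiobook |
| Exercise-only (E) | audiobook | treadmill |
| Med&Exer (C) | meditation | treadmill |

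**Parameters.** Let m = meditation versus audiobook in the 15-minute block, x = exercise versus rest, a = audiobook versus rest in the 30-minute block, and i = the meditation-by-exercise interaction. Day 1 training follows the same split: sessions "discuss the potential of and use of mindfulness and meditation (in the meditation groups only", and stress management in the other two arms. So m includes that training.

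**Arm means relative to N:** N = 0; M = m + a; E = x; C = m + x + i.

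**Contrasts that contain a:**

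- M - N = m + a
- C - M = (m + x + i) - (m + a) = x + i - a
- Interaction: (C - M) - (E - N) = (x + i - a) - x = i - a
- Main effect of meditation: [(C - E) + (M - N)]/2 = [(m + i) + (m + a)]/2 = m + i/2 + a/2
- Main effect of exercise: [(C - M) + (E - N)]/2 = [(x + i - a) + x]/2 = x + i/2 - a/2

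**Contrasts free of a:**

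- C - E = m + i (meditation added to exercise)
- E - N = x (exercise against rest)
- C - N = m + x + i (the whole package)

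**Identifiability.** Counting the intercept there are five parameters and four arms; the design matrix has rank 4. Meditation without exercise, the interaction, and a itself cannot be separated at any sample size. If no interaction is assumed (i = 0), four parameters remain and m can be estimated from C - E.

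**With a common 30-minute filler,** a drops out: M - N = m and the interaction contrast = i. In C - M and E - N, exercise is then measured against the same filler.

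**Exposure.** Over 20 sessions, 20 x 30 min = 600 min = 10 h, and 20 x 15 min = 300 min = 5 h. Nominal audiobook time is 10 h in M, 5 h in E, 5 h in N and 0 h in C. These are upper figures, because Table 1 places survey time inside some of the blocks. The block mismatched between M and N (10 h) is twice as long as the block meant to distinguish them (5 h).

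**The case against.** The strongest case on the other side is that the trial does not plan the affected analyses. Neither document announces a factorial or interaction analysis. Table 1 lists one experimental condition and three controls, section 8 is largely descriptive, and the SAP makes one two-group comparison. The sentence in section 2 about greater benefit goes on to say that feasibility is unknown, and greater benefit than either part does not require the effects to be more than additive. This stands, and it limits the consequence. It does not remove the point: section 4 hypothesises that meditation itself lowers disability, and section 8 allows effect sizes between arms, so meditation-only versus negative control is a natural figure to report.

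A reader might infer that the design cannot isolate meditation, or the added value of the combination, at all. The documents do not support that. Med&Exer and exercise-only share the treadmill block and differ in the 15-minute block, so their difference estimates meditation given exercise, which is also what the combination adds to exercise alone. Med&Exer versus meditation-only also remains a valid randomised comparison of two regimens as delivered; only its reading as exercise against rest fails.

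A reader might also infer that any audiobook effect passes in full into the daily pain VAS. Section 4 ties those ratings to before and after the meditation in meditation-only and the audiobook in the negative control, so they may not span the 30-minute filler. State anxiety, rated before and after each session, may span it. For the primary outcome, the RMDQ, the documents say nothing about the size of a, and it may be small.

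Finally, a common filler would leave the different Day 1 training in place, so the meditation contrast would still be a package. That is correct, but the training follows the meditation factor consistently and does not create this confounding.

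**Conclusion.** The mismatch is real, is stated twice and is unexplained. It shifts meditation-only versus negative control by a, the interaction by -a, and the main effects of meditation and exercise by a/2 and -a/2. It also makes Med&Exer versus meditation-only a test of exercise against an audiobook. The documents do not allow a to be sized; if a is zero there is no bias.

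The three contrasts Med&Exer versus exercise-only, exercise-only versus negative control, and Med&Exer versus negative control are untouched. It would be wrong to conclude that the SAP's primary result is compromised: that holds only if its unnamed control is meditation-only, and then only for reading the result as exercise against rest. If the control is the negative control or exercise-only, a does not enter. How the larger study analyses the remaining arms cannot be seen from these documents.

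This is a modest weakness of interpretation in an exploratory trial. It merits action because analysis cannot repair it and a small change of wording can.

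**What to change.** In Table 1 and in the matching paragraph of section 3, specify the same 30-minute filler for meditation-only and the negative control: audiobook in both, or rest in both. Audiobooks are already used in three arms, so this needs no extra visits, staff or session time. The small downside, if the audiobook is chosen, is that the negative control loses its rest period and exercise is judged against an audiobook.

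If participants have already been enrolled under the current text, leave the arms as they are. State in the analysis plan that inference about meditation rests on Med&Exer versus exercise-only. Report meditation-only versus negative control, and any factorial or interaction estimate, as confounded by the filler. Describe Med&Exer versus meditation-only as exercise against an audiobook. This costs a few sentences.

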All participants in the meditation groups will complete the Freiburg Mindfulness Inventory (FMI) at the beginning of their first day of exercise/meditation and on the last day of the trial. The FMI is a 30-item tool that assesses an individual's experience with meditation and mindfulness. For this feasibility study, data from the FMI will be particularly useful in evaluating whether there were any changes in mindfulness that developed during the trial. Failure to increase mindfulness during the trial might be a sign that a patient failed to "buy in" to the meditation intervention. We will also evaluate the likelihood of a patient to continue to meditate (or exercise) using a qualitative exit survey given on day 29. There are no safety concerns associated with the FMI or custom exit survey.

Assessment – Anxiety

To account for changes in anxiety during the current exploratory trial, we will use the State-Trait-Anxiety Inventory (STAI) form Y to evaluate state anxiety and the Fear-Avoidance Beliefs Questionnaire (FABQ) to evaluate fear avoidance behavior. Subjects will report their state anxiety (using a survey) before and after each trial. FABQ will be evaluated on day 1 and day 29. There are no serious safety concerns associated with this survey.

Assessment - Exercise

As described above, we will be using multiple assessment tools to evaluate physical fitness and exercise in this trial. General fitness will be determined by the International Physical Activity Questionnaire – Short Form (IPAQ-short) and a clearance of physical readiness for exercise will be determined by the AHA/ACSM Health/Fitness Facility Pre-participation Screening Questionnaire. Exercise exertion will be measured daily through active heart rate monitoring during exercise and the Borg Rate of Perceived Exertion (Borg RPE)⁸. Finally, throughout the 4 week trial, participants will be asked to wear wrist-based health activity monitors. These watches monitor and record activity and other factors. There are no serious safety concerns associated with these surveys or monitoring methods.

5. Sample selection

Adults with chronic low back pain who are otherwise healthy will be recruited for participation in this study. The AHA screening questionnaire will be administered during the screening process to determine whether potential subjects meet the inclusion/exclusion criteria.

Eligibility Criteria:

Inclusion criteria

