Title Page:

Statistical Analysis Plan

Combined exercise and meditation as a treatment for patients with chronic back pain

NCT number not available

12/21/17

Statistical Analysis Plan
Combined exercise and meditation as a treatment for patients with chronic back pain

This is a single-blind, single center randomized clinical trial comparing a treatment group (MedExT) versus a control group. The current analysis plan is specific to this study for reporting and publication purposes but is part of a larger study. The primary outcome of this study is to compare the post Roland-Morris Disability Questionnaire scores between the two independent groups. This will be achieved by comparing the mean post disability score for the MedExT group to the mean post disability score for the control group using a two-sample t-test (or the Mann-Whitney-Wilcoxon rank sum test if normality does not hold) in which a one-sided p-value < 0.05 will be considered a significant improvement in the MedExT group.

Three secondary treatment responses will be studied. The first will test whether the MedExT group will significantly increase mean scores on the Freiburg Mindfulness Inventory as determined by a two-sample t-test or the Rank Sum test given distributional properties of the data ($P < 0.05$). The second will explore whether the MedExT treatment will significantly influence a mean change in responses on the three psychological inventories administered; the Fear Avoidance Beliefs Questionnaire, the STAI state anxiety inventory and the STAI state trait inventory, $p < 0.02$. The third outcome measured will study mean response changes in the series of 14 Quantitative Sensory Tests measured at baseline and at the completion of the 4-week intervention period. Significant mean pre/post differences between groups will be identified using the two-sample t-test or the Rank Sum test where appropriate adjusting the significance level to 0.005. Additionally two pain outcome measures will be repeatedly observed throughout the study taken at baseline and on each intervention day. These measures are the VAS pain intensity score and the VAS pain unpleasantness. A repeated measures multivariate analysis of variance (MANOVA) procedure will be used to determine if the vector of timed responses is significantly different between the two study groups.

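### The first FMI reading comes on Day 2, after the Day 1 mindfulness training, so any effect of that training would be missing from measured FMI change

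*Protocol*

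**What the plan says.** Four statements in the protocol fix the order of events.

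- **Training.** Section 3 (Intervention Sessions): "All participants will receive a 45 min meditation and stress training session following baseline pain testing", on the intake day, Day 1. Content differs by arm. The sessions "discuss the potential of and use of mindfulness and meditation (in the meditation groups only"); the exercise-only and negative-control groups hear about stress management instead. Section 1 lists meditation training, followed by guided meditation, in its description of the experimental condition.
- **First FMI.** The same part of section 3 says "they will complete the Freiburg Mindfulness Inventory (FMI) meditation survey immediately prior to their first meditation before exercise". Section 4 (Assessment - Meditation and Mindfulness) agrees, and limits the inventory to the two meditation arms, whose members "will complete the Freiburg Mindfulness Inventory (FMI) at the beginning of their first day of exercise/meditation and on the last day of the trial".
- **First session.** Section 3 places the supervised treadmill sessions "on day 2 (first day of intervention), day 9, day 16, and day 23", so the first FMI falls on Day 2.
- **Final FMI.** Section 3 says "The FMI will be used again on day 27"; section 4 says the last day of the trial.

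Section 4 uses the FMI to judge whether mindfulness changed over the trial, and treats a failure to rise as a possible sign that the patient did not engage with the meditation. The SAP's first secondary response asks whether "the MedExT group will significantly increase mean scores on the Freiburg Mindfulness Inventory", using a two-sample t-test or rank sum test at P < 0.05. It names no reference time point for the FMI.

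**The concern.** A change score needs a starting value taken before the treatment begins. Here the meditation groups receive an arm-specific, psychologist-led session on mindfulness before anyone completes the FMI. Other Day 1 measures are better placed: pain testing explicitly precedes the training, and the activity and state anxiety questionnaires belong to the intake procedures. The FMI, which is the measure closest in content to the training, comes after it.

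Two uses are exposed. The first is the individual reading of engagement in section 4. A participant who responded strongly to the Day 1 session could start high on Day 2, show little further rise, and be taken for someone who did not engage. The second is the SAP's FMI test, if it uses change from the first reading or adjusts for it. Because the training differs by arm, allocation must already be known on Day 1. The Day 2 score is therefore a post-allocation value, and adjusting for it could remove part of the treatment effect.

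A pre-training score cannot be recovered later, so this has to be settled before the intake visit.

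**Working it through.** The documents give no FMI effect size, standard deviation, sample size or power, so there is no figure to reproduce. The check is first of sequence, then of how much could be at stake.

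**Sequence**

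| Day | Event | Source (protocol) |
|---|---|---|
| 1 | Consent, intake surveys, baseline pain testing | Section 3, Figure 1 |
| 1 | 45-minute session; mindfulness content in meditation groups only | Section 3, Intervention Sessions |
| 2 | First FMI, then first guided meditation | Sections 3 and 4 |
| 27, or last day of the trial | Final FMI | Section 3; section 4 |

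Could an FMI be hidden among the Day 1 surveys? The Day 1 questionnaires named in the text cover activity level and state anxiety (section 3) and fear-avoidance beliefs (section 4). Figure 1 mentions intake surveys without naming them, but both statements about the first FMI place it on the first exercise/meditation day. No pre-training FMI is described.

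**Exposure before the first reading**

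Sessions: 4 weeks × 5 = 20. At about 15 minutes each, 20 × 15 = 300 minutes of guided meditation. The training share of total contact time is 45 / (45 + 300) = 45/345 ≈ 13%. This measures exposure; nothing in the documents links minutes to FMI points.

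**Attenuation of a change score**

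Let f be the share of the total FMI gain that occurs before the first reading. Then measured gain = (1 − f) × total gain. At f = 0 nothing is lost.

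**Illustrative power**

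The assumptions, none of them from the documents, are: 80% power for the full gain, a change-score analysis, unchanged SD, no training effect on FMI in the control arm, and the normal approximation. The SAP does not state the sidedness of the FMI test, so both are shown.

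Power = Φ[(1 − f)(z_α + 0.842) − z_α], with z_α = 1.960 two-sided or 1.645 one-sided at 0.05. For example, at f = 0.10 two-sided: 0.90 × 2.802 − 1.960 = 0.562, and Φ(0.562) = 0.713.

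| f (assumed) | Measured share of gain | Power, two-sided 0.05 | Power, one-sided 0.05 |
|---|---|---|---|
| 0 | 100% | 80% | 80% |
| 0.10 | 90% | 71% | 72% |
| 0.25 | 75% | 56% | 59% |
| 0.50 | 50% | 29% | 34% |

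The lower rows only show how the formula behaves. No source supports f as high as 0.50, or any other particular value.

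**Which analyses use the Day 2 reading**

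The SAP speaks of mean change for the psychological inventories and of pre/post differences for the sensory tests. For the FMI it speaks only of increasing mean scores, and its primary outcome is a comparison of post scores. The FMI test could therefore be of either kind:

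- final minus Day 2, or final adjusted for Day 2: any training effect is wholly or partly removed;
- final scores compared between arms: the Day 2 reading is not used, and any training effect stays in the difference.

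**The case against.** The strongest reply is that Day 2 is the right origin for a narrower question. Section 3 introduces the FMI as a way to evaluate the effect of the meditation, treats Day 2 as the start of intervention, and separates the training from the later intervention days. For the effect of the recordings alone, a reading just before the first one is defensible. It would also keep any change in how novices understand the items, brought about by the training, out of the measured gain. This stands as far as it goes, but the plan does not state that narrower aim. Section 1 counts training as part of the experimental condition, and the SAP tests MedExT as a whole.

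A reader might infer more than the documents support:

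- *That some of the FMI gain is certainly lost.* No statement shows that one session, described as a discussion with no practice mentioned, moves the FMI at all.
- *That the SAP's FMI test is necessarily biased.* The SAP does not say that it uses change scores, and a comparison of final scores would escape the problem.
- *That the loss could be large because 45 minutes equals three recordings.* Against all 20 sessions it is about 13% of contact time, and contact time is not effect.
- *That a false positive could result.* If the training raises FMI in the meditation groups, the error understates their gain.

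It is also fair to say that the FMI is a secondary measure in a feasibility trial whose primary outcome is the Roland-Morris questionnaire. Section 4 gives the FMI to the meditation groups only while the SAP compares two groups on it. That is a separate and possibly larger problem, which moving the first reading would not solve.

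**Conclusion.** The point holds in conditional form. The protocol takes its only FMI reading before guided practice on Day 2, after arm-specific mindfulness training on Day 1. Any effect of that training would already be in the first reading. It would be missing from section 4's assessment of change and engagement, and from the SAP's FMI test if that test uses change or baseline-adjusted scores. A test of final scores alone would not be affected.

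The size is unknown and may be zero. The tempting stronger conclusion, that part of the effect under test definitely falls before the first reading, is not supported. What is established is where such an effect would fall, and not that there is one. The sequence is certain on the documents; the impact is not. Severity is low to moderate. The change is worth making because it is cheap and the missing value cannot be collected afterwards.

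**What to change.** 1. In protocol sections 3 and 4, place the first FMI on Day 1, after consent and before the training session.
2. In the SAP, define FMI change as the final score minus the Day 1 pre-training score, and state whether the two-sample test uses that change, a baseline-adjusted score or the final score.
3. Separately, reconcile the final FMI date. Section 3 gives day 27; section 4 gives the last day of the trial. Section 3 describes the trial as lasting 29 days, but section 4 also uses the word trial for single sessions, so the intended day is unclear. Set one day for everyone. Setting may differ too, since Day 27 can be done at home while Figure 1 shows Day 29 in clinic.

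The cost is a few more minutes at intake and short wording changes in both documents. Days 1 and 2 are both in-clinic visits, so no visit is added. For anyone enrolled before the change, the pre-training score cannot be reconstructed, and the report should say so.
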